- Sign an IRB-approved informed consent document.
- Age ≥ 18 years.
- IPSS low- or intermediate-1–risk MDS, including CMML-1
- ECOG performance status of ≤ 3 at study entry.
- Organ function as defined below:
 - Serum creatinine ≤ 2 mg/dL
 - Total bilirubin $\leq 2 \times$ ULN
 - ALT (SGPT) $\leq 2 \times$ ULN
 - AST (SGOT) $\leq 2 \times$ ULN

- Women of childbearing potential must have a negative serum or urine pregnancy test within 7 days and will also need to use contraceptives. Men must agree not to father a child and agree to use a condom if his partner is of child bearing potential.

Exclusion Criteria:

- Breast feeding females
- Prior therapy with decitabine or azacitidine

V. Treatment plan

1. Study design

Transfusion-dependent subjects will be randomized to AZA 75 mg/m² IV/SC for 5 days, AZA 75 mg/m² IV/SC for 3 days, or DAC 20 mg/m² IV for 3 days on an even basis at the beginning, then, based on efficacy and following a Bayesian design, patients will be assigned to the superior arm.

Transfusion-independent subjects will be randomized to either BSC or one of the 3 arms mentioned above on an even basis at the beginning, then, based on efficacy and following a Bayesian design, patients will be assigned to the superior arm.

Transfusion-independent subjects assigned to BSC will be assigned to one of the 3 above arms once they start requiring blood transfusion. That would be considered an event.

Transfusion-dependent group will be defined as patients requiring blood transfusion for MDS or CMML-1 at any time.

2. Treatment plan

Patients will be randomized to receive:

Decitabine 20 mg/m² IV daily for 3 days (days 1-3) approximately every 28 days

or

Azacitidine 75 mg/m² SC or IV daily for 3 days (days 1-3) approximately every 28 days

or

Azacitidine 75 mg/m² SC or IV daily for 5 days (days 1-5) approximately every 28 days

or

BSC (for transfusion-independent subjects only)

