Patients may receive their second course of therapy without interruption, regardless of their degree of myelosuppression. After the first course of therapy, the interval between subsequent cycles of therapy could be shortened or prolonged at the discretion of the investigator. Subsequent cycles can be given prior to peripheral blood count recovery if considered to be in the best interest for the patient and after discussion with the principal investigator and the discussion documented in the patient's medical record. If study drug related prolonged myelosuppression (≥ 42 days of absolute neutrophil count [ANC] $< 1 \times 10^9/L$ and platelet count $< 30 \times 10^9/L$) is observed after cycle 2, subsequent cycles may be given at the next lower dose (DAC, 15 mg/m²/day, then 10 mg/m²/day, then 5 mg/m²/day; AZA, 56 mg/m²/day, then 37 mg/m²/day, then 18 mg/m²/day) after recovery (ANC $\geq 1 \times 10^9/L$ and platelet count $> 50 \times 10^9/L$) and subsequent cycles of

AZA. Granulocyte-colony stimulating factor for fever of unknown origin, infection, and/or ANC $<0.75 \times 10^9/L$ can be administered.

Dose reductions can also be made in other clinical situations where this step is considered to be in the best interest for the patient and after discussion with the principal investigator and the discussion documented in the patient's medical record. The following table is a suggestion for dose modifications in subsequent treatment courses:

Table 1: Dose levels adjustment

Dose level	AZA (mg/m ²)	DAC (mg/m ²)
-1	56	15
-2	37	10
-3	18	5

VI. BASELINE AND PER-TREATMENT EVALUATION

Baseline

1. A complete history and physical examination within 14 days prior to study entry.
2. CBC, differential platelet count.
3. Creatinine, bilirubin, ALT or AST,
4. Bone marrow aspirate and/or biopsy with cytogenetics (if bone marrow not done within 6 weeks and cytogenetics (if previously abnormal) within 3 months prior to study entry.

5. Serum or urine pregnancy test within 7 days of treatment start for women of childbearing potential
6. Documentation of frequency of transfusions (PRBC and Platelets) prior to start of each cycle
7. Documentation of any prior administration of growth factors and ESA

Prestudy laboratory tests must be obtained within 14 days of registration.

During therapy

1. CBC, differential, and platelet count once monthly prior to start of each cycle
(the differential may be omitted when the WBC is $< 0.5 \times 10^9/L$)

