Supportive measures such as prophylaxis for tumor lysis syndrome, analgesics, blood transfusions, antimicrobials and G-CSF for fever/infection are permitted as clinically indicated. Growth factor and ESA administration while on study will be documented.

VII. STUDY END POINTS

Primary:

1. Event-free survival rates of two different drugs DAC versus AZA on an abbreviated schedule and a standard arm of AZA given over 5 days in patients with low-risk MDS transfusion-dependent and to BSC in patients with low-risk MDS transfusion-independent. Events are defined as no response, loss of response, progression to higher risk category MDS, transformation to AML, discontinuation of therapy due to side effects, or death.

Secondary:

1. Overall improvement rate (OIR), defined as complete remission (CR), partial remission (PR), marrow CR (mCR), or hematologic improvement (HI), measured using each patient's best response with the 2 different agents. Response will be

assessed using the modified MDS International Working Group 2006 criteria. The best response within the first two cycles will be the OIR for each treatment arm that will be used in the adaptive randomization algorithm.

2. Transfusion independence (defined as being transfusion-free for ≥ 8 consecutive weeks between the first dose and study treatment discontinuation)
3. Cytogenetic response, if applicable
4. Clinical benefit
5. Duration of response
6. Time to transformation into AML
7. Overall survival
8. Safety profile

VII. CRITERIA FOR WITHDRAWAL

Reasons for withdrawal include:

- Withdrawal of consent or the subject refuses to continue treatment and/or procedures/observations.
- Relapse/progression unless the treating physician determines that the patient has achieved clinical benefit, at which time further therapy on protocol may be permitted with approval from the PI and the discussion documented in the patient's medical record.
- No response after at least 6 courses unless the treating physician determines that the patient has achieved clinical benefit, at which time further therapy on protocol may be permitted with approval from the PI and the discussion documented in the medical

record. A bone marrow biopsy and/or aspirate is required to confirm that the patient has not achieved a response.

- Intercurrent illness preventing further administration of protocol treatment,
- Unacceptable toxicity that in the opinion of the investigator makes continued therapy unsafe.

VIII. CRITERIA FOR RESPONSE

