The response criteria recommended by the MDS International Working Group 2006.

Responses must be verified, documented, and signed in the local medical record by the local PI. (Patients are considered non evaluable if they have received less than 2 courses of treatment, unless there is clear disease progression.)

Definitions:

Complete Response (CR):

Bone marrow: $\leq 5\%$ myeloblasts with normal maturation of all cell lines; persistent dysplasia will be noted

Peripheral blood:

Hgb ≥ 11 g/dL

Platelets $\geq 100 \times 10^9/L$

Neutrophils $\geq 1.0 \times 10^9/L$

Blasts 0%

Partial response (PR):

All CR criteria if abnormal before treatment except: bone marrow blasts decreased by $\geq 50\%$ over pretreatment but still $> 5\%$

Marrow CR:

Blasts \leq 5% and decrease by \geq 50% from baseline (baseline blasts should be above 5% to be eligible for marrow CR)

Hematologic Improvement (HI): (responses must last at least 8 weeks)

Erythroid response [HI-E; (if pretreatment Hgb $<$ 11 g/dL)]; Hgb increase by \geq 1.5 g/dL; Relevant reduction of units of RBC transfusions by an absolute number of at least 4 RBC transfusions/8 weeks compared with the pretreatment transfusion number in the previous 8 weeks. Only RBC transfusions given for a Hgb of \leq 9.0 g/dL pretreatment will count in the RBC transfusion response evaluation.

Platelet response [HI-P; ((if pretreatment Platelet count $<$ $100 \times 10^9 /L$)]: Absolute increase of $\geq 30 \times 10^9 /L$ for patients starting with $> 20 \times 10^9 /L$ platelets, or increase from $< 20 \times 10^9 /L$ to $> 20 \times 10^9 /L$ and by at least 100%.

Neutrophil response [HI-N; (pretreatment, ANC $< 1.0 \times 10^9 /L$)]: At least 100% increase and an absolute increase $> 0.5 \times 10^9 /L$

Progression/Relapse after hematological improvement: ≥ 1 of the following: $\geq 50\%$ decrement from maximum response levels in granulocytes or platelets; \downarrow in Hgb by ≥ 1.5 g/dL; transfusion dependence

Stable Disease: Not satisfying criteria for Complete Remission, Partial Response, Marrow CR, Hematologic Improvement or Progression/Relapse.

IX. REPORTING REQUIREMENTS

All adverse and serious adverse events will be recorded and reported according to the Leukemia-Specific Adverse Events (appendix A). The MD Anderson Leukemia

Department will report SAEs in accordance with MD Anderson IRB policies and procedures and Appendix A of the protocol.

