This is an adaptive randomized phase II trial for low-risk MDS patients. Regarding the patients transfusion status, patients can be categorized as transfusion dependent and transfusion independent patients. It is expected that there will be half of the transfusion-dependent patients and half of transfusion-independent patients. For transfusion dependent patients, the goal is to compare three treatment arms: 1) DAC, 2) AZA3 (treatment of 3 days), and 3) AZA5 (treatment of 5 days). For transfusion independent patients, the goal is to compare four treatment arms: 1) best supportive care (BSC) 2) DAC, 3) AZA3 (treatment of 3 days), and 4) AZA5 (treatment of 5 days). The primary outcome is event free survival (EFS) defined as the time from beginning of treatment till an event occurs or last follow-up. For transfusion independent patients, the events includes lack of response, requirement of blood transfusion, progression to advanced stages of disease, transformation into AML, discontinuation of therapy due to side effects, and death. The patients who change from transfusion independence to transfusion dependence under BSC will be enrolled in transfusion-dependent group and adaptively assign to the three treatment arms, that is, DAC, AZA3, or AZA5. For transfusion dependent patients, the events includes lack of response, progression to advanced stages of disease, transformation into AML, discontinuation of therapy due to side effects, and death.

Study design

The maximum number of patients accrued will be 240. There will be two parallel adaptive randomization trials for transfusion dependent (N=120) and transfusion independent (N=120) patients respectively. Since we are expecting patients under BSC

will eventually become the transfusion dependent, it is assumed that initially there will be 120 patients under transfusion-dependent group, and the total number increases to about 150 after enrolling the approximate 30 patients under BSC.

Part I Transfusion dependent patients (N=150)

Design

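### The transfusion-independence endpoint sets no baseline transfusion need and no denominator, so patients who merely stay transfusion-free can be counted as achieving independence

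*Combined protocol and SAP*

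**What the plan says.** All references are to the combined protocol and SAP.

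- **Stratum (V. Treatment plan, 1. Study design):** "Transfusion-dependent group will be defined as patients requiring blood transfusion for MDS or CMML-1 at any time". There is no look-back window, minimum number of units or haemoglobin trigger. The General Description in XII says only that "patients can be categorized as transfusion dependent and transfusion independent patients" and does not define either group further.
- **Who receives drug (same section):** "Transfusion-independent subjects will be randomized to either BSC or one of the 3 arms mentioned above". Transfusion-independent patients on a drug arm therefore have a first dose.
- **Endpoint (VII. Study End Points, Secondary, item 2):** transfusion independence is "defined as being transfusion-free for ≥ 8 consecutive weeks between the first dose and study treatment discontinuation". No pretreatment need is required, and neither a stratum nor a denominator is named.
- **Erythroid response (VIII. Criteria for Response):** the transfusion limb of HI-E needs a fall of at least 4 RBC transfusions per 8 weeks, "compared with the pretreatment transfusion number in the previous 8 weeks". This is the plan's only rule that uses a baseline transfusion count.
- **Data collected (VI. Baseline and Per-Treatment Evaluation):** "Documentation of frequency of transfusions (PRBC and Platelets) prior to start of each cycle". Table 2 also asks for transfusion history before study entry. No threshold is applied to either.
- **Analysis Plan (XII):** efficacy is analysed by intention to treat in all patients. No subset is named for this endpoint.

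**The concern.** The Rationale names relief of transfusion needs as an aim of treatment in lower-risk MDS, and this endpoint measures that aim most directly. As defined, it cannot tell a patient who becomes transfusion-free from one who already was.

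Two kinds of patient are affected. The first is a patient placed in the dependent stratum for a past transfusion who has no current need. The second is a transfusion-independent patient on a drug arm in Part II, who satisfies the wording by continuing as at entry for 8 weeks. Counting either as a success raises the reported rate without any benefit from treatment. Because such patients occur in every arm, they also pull the arms' rates together.

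The plan's two measures of transfusion benefit also disagree. A patient with no RBC transfusion in the 8 weeks before treatment cannot meet the transfusion limb of HI-E, yet can meet transfusion independence with no change at all.

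**Working it through.** **1. Is there a repair elsewhere?** The plan states no rate, power or sample size for this endpoint, so there is no figure to reproduce. The check is whether any section adds a baseline requirement or a denominator. Section V defines the stratum without a window. Section VI records transfusions but sets no threshold. The 8-week comparison in Section VIII belongs to HI-E alone. Section XII, including the Analysis Plan, names no evaluable subset. Nothing fills the gap.

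**2. Size, on assumed inputs.** Let f be the share of analysed patients with no recent transfusion need, s the share of those who stay transfusion-free for 8 weeks, and p the true rate in the rest.

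Reported rate = f × s + (1 − f) × p

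None of f, s or p is in the documents. Assume p = 30%, a true difference of 20 points among patients with need, and f from 10% to 40%. Set s = 100% in every arm, which gives the largest possible inflation. Then the rate is f + (1 − f) × 0.30 and the difference is (1 − f) × 20 points.

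| f | Reported rate | Reported difference |
|---|---|---|
| 0.10 | 0.10 + 0.90 × 0.30 = 37% | 0.90 × 20 = 18 points |
| 0.20 | 0.20 + 0.80 × 0.30 = 44% | 0.80 × 20 = 16 points |
| 0.30 | 0.30 + 0.70 × 0.30 = 51% | 0.70 × 20 = 14 points |
| 0.40 | 0.40 + 0.60 × 0.30 = 58% | 0.60 × 20 = 12 points |

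With s below 100% the inflation is f × (s − p), which is smaller. The difference column assumes that patients without need contribute no contrast between arms.

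**3. Would requiring just one recent transfusion be enough?** Suppose transfusion episodes follow a Poisson process with a constant mean of r per 8 weeks and no drug effect. The withdrawal rule for non-response reads "No response after at least 6 courses unless the treating physician determines that the patient has achieved clinical benefit". Six courses of about 28 days give 6 × 4 = 24 weeks on treatment. The chance of at least one 8-week gap is then

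P = e^(−r) × (1 + 2r) − e^(−2r) × (r + r²/2)

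- r = 0.5: 1.213 − 0.230 = 98%
- r = 1: 1.104 − 0.203 = 90%
- r = 2: 0.677 − 0.073 = 60%
- r = 4: 0.165 − 0.004 = 16%

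A simulation with 100,000 runs gave 98%, 90%, 60% and 16%. With only 8 weeks on treatment the chance is e^(−r): 61%, 37%, 14% and 2%. So a single recent transfusion is a weak filter. Patients with low need can meet the endpoint by chance, more so the longer they stay on treatment.

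**The case against.** The strongest reply is that little depends on this endpoint. It is one of eight secondary endpoints and has no stated rate, power or decision rule. Arms are selected and dropped on EFS. Section VII also names the overall improvement rate as an input to adaptive randomization, but never transfusion independence. HI-E, which contributes to that rate, already has a baseline-referenced transfusion limb. Assignment within each stratum is randomized. All of this stands, and it limits the consequence to how this endpoint is reported and interpreted.

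Several stronger readings are tempting, and the documents do not support them:

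- **That one transfusion years ago certainly makes a patient dependent.** The rule follows directly on the provision for BSC patients who come to need transfusion, so its open time reference may also cover need arising on study. The wording is ambiguous. The gap does not hinge on it, because the endpoint would still include drug-arm patients of Part II under any stratum definition.
- **That patients without need succeed whatever the drug does.** Section III lists myelosuppression as decitabine's major toxicity and as common with azacitidine. Such a patient can fail by needing transfusion or by stopping before 8 weeks. Setting s = 100% is therefore a bound, not an estimate.
- **That transfusion-independent patients meet the endpoint at baseline.** The period begins at the first dose, so nobody can. BSC patients have no first dose while on BSC, so the endpoint is undefined for them there.
- **That the EFS comparison is compromised.** The selection rules do not use this endpoint.

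**Conclusion.** The concern holds as a defect in the endpoint definition, made worse by an ambiguous stratum definition. Followed as written, the rule credits patients who had no current transfusion need with achieving independence, and no other section prevents this. The direction is clear as long as such patients stay transfusion-free more often than patients with need become so: the rate is too high and, unless patients without need themselves differ between arms, the contrasts are too small.

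The size is not known. The 37-58% rate and 18-12 point difference are upper-bound illustrations. They rest on an assumed 10-40% share without recent need, all of whom succeed, and on an assumed 30% true rate and 20-point true difference in the rest. The chance-gap figures rest on a constant Poisson transfusion rate and 24 weeks on treatment. The change should be made because it is cheap and the endpoint addresses a stated aim of therapy, but it does not alter the trial's primary decision rules.

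**What to change.** 1. Restrict the transfusion-independence denominator to patients with a documented transfusion need in a fixed window before the first dose, for example the 8 weeks already used for HI-E. The sponsor should set the minimum count, bearing in mind that a low count leaves many chance successes.
2. Count RBC and platelet transfusions, and analyse them by type. Both are recorded, and an RBC-only rule would leave out patients who need platelets.
3. Report the number of such patients in each arm alongside the rate.
4. In Part II, report maintained transfusion-freedom as a separate outcome and do not label it achieved independence.
5. State in Section V what period the stratum definition covers.
6. Acknowledge in the report that 8-week gaps can still occur by chance among patients with low need.

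The endpoint changes need only definition and analysis wording, with no new visits. They use the transfusion history already collected and the 8-week pretreatment count that HI-E already requires. The cost is a smaller denominator and so less precision. The patients who remain are those for whom the endpoint has meaning.

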2. Creatinine, bilirubin, ALT or AST once monthly prior to start of each cycle.
3. Bone marrow aspirate and/or biopsy to confirm response, to be performed after cycle 2 then every 3 cycles for the first year, then every 6 cycles thereafter.
All bone marrows will be performed by the registering center, not in the local MD office.
4. Conventional cytogenetics to be performed after cycle 2 then every 3 cycles for the first year, then every 6 cycles thereafter
5. Documentation of frequency of transfusions (PRBC and Platelets) prior to start of each cycle.
6. Documentation in the medical record of any grade 3 or higher possibly, probably, definitely related adverse events that have occurred prior to start of each cycle. For guidelines on SAE Reporting and AE entry for Case Report

Forms (CRF), please refer to Appendix A (for MD Anderson) and Appendix G (for Participating Institutions).

7. Documentation of any prior administration of growth factors and ESA prior to start of each cycle

Table 2: Evaluation

Test	Pre-treatment	During treatment
CBC, differential platelet count	within 14 days of treatment start	Monthly prior to start of each cycle (+/- 7 days)
Creatinine, bilirubin, ALT or AST	within 14 days of treatment start	Monthly prior to start of each cycle (+/- 7 days)
Bone marrow aspirate	Within 6 weeks prior to study entry	after cycle 2 then prior to every 3 cycles for the first year, then prior to every 6 cycles thereafter
Cytogenetics	Within 3 months prior to study entry	after cycle 2 then prior to every 3 cycles for the first year, then prior to every 6 cycles thereafter
Serum or urine pregnancy test for woman of childbearing potential	within 7 days of treatment start	
Transfusion history documented	Prior to study entry	Prior to start of each cycle
Growth factors and ESA documentation	Prior to study entry	Prior to start of each cycle

Follow-Up

Following completion of active treatment and while still on study, patients will be followed for survival approximately every 6 to 12 months for up to 5 years. This follow up can either be done as a visit to the study doctor's clinic or via telephone call to the patient.

Chemotherapy administration

If the study doctor decides it is acceptable, enrolled subjects may be allowed to receive treatment from their local cancer doctor following cycle 1 (appendix B). However, enrolled subjects will have to return to the study doctor's clinic at least every 3 cycles for study visits.

Supportive care

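### EFS start is undefined for BSC and never-dosed patients, and marrow-detectable progression is scheduled to be looked for only in the drug arms of Part II

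*Combined protocol and SAP*

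**What the plan says.** **Start of EFS.** Section XII, General Description, gives "event free survival (EFS) defined as the time from beginning of treatment till an event occurs or last follow-up". No randomization or registration date is named as the start. The Analysis Plan puts all patients in the intent-to-treat efficacy analysis.

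**Events.** For transfusion-independent patients the same section lists, among others, "requirement of blood transfusion, progression to advanced stages of disease, transformation into AML". Lack of response, discontinuation for side effects and death complete the list.

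**Assessments.** Section VI and Table 2 place the on-study checks under therapy or treatment:
- Marrow and cytogenetics: "after cycle 2 then prior to every 3 cycles for the first year, then prior to every 6 cycles thereafter".
- Blood count and chemistry: "Monthly prior to start of each cycle (+/- 7 days".
- Transfusions: "Documentation of frequency of transfusions (PRBC and Platelets) prior to start of each cycle". Growth factors follow the same timing.
- Return visits for patients treated locally: "clinic at least every 3 cycles for study visits".

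The only follow-up not tied to cycles is for survival, every 6 to 12 months after active treatment ends, and may be by telephone.

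**BSC.** Section V describes no cycles or visits for this arm. It does say: "Transfusion-independent subjects assigned to BSC will be assigned to one of the 3 above arms once they start requiring blood transfusion". Section XII expects about 30 such patients to enter Part I.

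**The concern.** Part II compares three drug arms with BSC on EFS, and the accumulating EFS data drive allocation, arm dropping and selection. That works only if follow-up starts at a comparable date in each arm and events are looked for in a comparable way.

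Section II says that IPSS risk depends on cytopenias, marrow blasts and karyotype. Part of any progression to a higher-risk category therefore cannot be seen without a marrow. If marrows are scheduled in three arms only, a BSC patient who progresses in the marrow stays event-free in the data until the disease shows clinically. A later analysis can describe that difference, but it cannot undo the assignments already made from it.

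The missing start date is a separate gap. A patient randomized to drug who never receives a dose has no EFS time under the definition, yet belongs in the analysis.

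**Working it through.** **1. The schedule, arm by arm**

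| Item | Drug arms | BSC |
|---|---|---|
| EFS start | first dose | not defined |
| Blood count, chemistry | monthly, before each cycle | no cycles; the monthly term might be carried over |
| Transfusion, growth-factor record | before each cycle | no schedule; a first transfusion triggers reassignment |
| Marrow, cytogenetics | after cycle 2, then every 3 cycles: 2, 5, 8, 11 | none stated |
| Follow-up outside cycles | survival only, after active treatment | no active treatment to complete |

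In the first 11 cycles a drug patient has 4 scheduled marrows. For BSC the text schedules none.

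**2. The plan's own figures**

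The Part II design was simulated with 1,500 trials per scenario. The settings were exponential EFS, the inverse gamma (2.14, 13.73) prior, 10 patients per arm first, square-root allocation with a floor of 0.1, arm dropping against 12 months, early selection above 0.975 and final selection above 0.8. Arms below 0.025 were suspended, as Part I describes.

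- Scenario 1, probability of selecting BSC: 0.039 (Table 6: 0.037).
- Scenario 5, probability of selecting AZA5: 0.784 (Table 6: 0.797).

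The early-stopping rows were not reproduced. Arms stopped in scenario 1 came to about 0.39 against about 0.24, and early selection in scenario 5 to 0.247 against 0.059. They depend on software details that the documents do not give.

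**3. Effect of late detection on the BSC median**

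Inputs from the plan: true median 12 months, so λ = ln2/12 = 0.05776 per month; 120 patients at 4 per month, so 30 months of accrual; 12 months of further follow-up. Assumptions: a fraction f of the hazard is marrow-only, and such an event surfaces D months late unless another event comes first. The documents give neither f nor D, so ranges are shown.

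With a = (1 − f)λ and complete follow-up:

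mean observed time = 1/λ + f × (1 − exp(−aD))/a, and fitted exponential median = ln2 × that mean.

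- f = 0.10, D = 3: a = 0.05199; (1 − exp(−0.1560))/a = 2.778; mean = 17.312 + 0.278 = 17.590; median = 12.19 months.
- f = 0.30, D = 12: a = 0.04043; (1 − exp(−0.4852))/a = 9.508; mean = 17.312 + 2.852 = 20.164; median = 13.98 months.

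With administrative censoring uniform between 12 and 42 months (12 plus 0 to 30), the fitted median is ln2 × E[min(T, C)] / Pr(T ≤ C), where T is the observed event time and C the censoring time. Evaluated numerically, ignoring the prior:

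| f | D = 3 | D = 6 | D = 12 |
|---|---|---|---|
| 0.10 | 12.3 | 12.5 | 12.8 |
| 0.20 | 12.5 | 13.0 | 13.8 |
| 0.30 | 12.8 | 13.5 | 14.8 |

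Censoring raises the figures because the detected-event rate is lowest in the first D months, which then carry more weight. Across both versions the range is about 12.2 to 14.8 months.

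**4. An outer bound on selection**

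Here all true medians are 12 months, drug arms are checked monthly, and every BSC event, including transfusion and death, is held back to a visit every 3, 6 or 12 months. The probability of wrongly selecting BSC is then 0.046, 0.153 or 0.637, against 0.039 with exact detection in all arms. Mean patients on BSC are 34.7, 42.6 or 46.9, against 30.0. The Monte Carlo standard error is at most about 0.013. The 3-month result cannot be told apart from the baseline.

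**The case against.** - **Time zero.** A reader might infer that BSC patients have no time zero at all. Section XII counts BSC among four treatment arms, and Section V lists it among what patients are randomized to receive, so the start of treatment could mean the assignment date. The text does not say so. Undefined is the right word.
- **Transfusion.** A reader might infer that transfusion need on BSC would be found only by chance. It is a dated clinical act that triggers reassignment, and Section X stresses timely recording of events. The exposed events are marrow-detectable progression and early AML.
- **Monthly counts.** Table 2 says monthly as well as before each cycle, and the Appendix B letter speaks of visits every three months. That letter concerns drug courses given locally and differs from the 3-cycle interval in Section VI, so the two should be reconciled. Neither gives BSC a marrow, cytogenetic or transfusion schedule.
- **Size.** Removing marrow-only events altogether gives 12/(1 − f) = 13.3, 15.0 or 17.1 months for f = 0.10, 0.20 or 0.30. That treats delayed events as never found, so those figures should not be used. Nor does Table 6 scenario 3 (7, 12, 15 and 20 months) declare 12 against 15 a meaningful gap. Step 4 also exceeds the concern, because it delays every BSC event.
- **Direction.** Lack of response is an event in this stratum. If it is counted on BSC, it shortens BSC EFS.
- **Re-entry.** A reader might infer that BSC patients enter Part I without a fresh marrow and that old progression is then charged to the drug. They are to be enrolled in the transfusion-dependent group, and the Section VI baseline already has a 6-week marrow window. Whether study entry there includes second entry is not stated.
- **Unseen text.** Some material, including Appendix G and the Data Quality Management Plan, is not available. The finding covers the available text only.

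What stands after this is the gap itself: no EFS start and no assessment schedule written for BSC.

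**Conclusion.** The gap holds on the available text and needs correcting before EFS data are used for allocation. EFS has no defined start for BSC or for never-dosed patients. Scheduled marrow and cytogenetic tests exist only in the drug arms, although progression and AML are primary events in all four.

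Taken alone, unequal detection lengthens observed BSC EFS: a true 12-month median is fitted as about 12.2 to 14.8 months. This assumes exponential EFS, 10% to 30% marrow-only events, and detection 3 to 12 months later than in the drug arms. Detection in the drug arms is treated as immediate; their marrows are in fact three cycles apart, which narrows the difference.

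A firm claim that selection is biased toward BSC would go too far. The documents fix neither the detection delay nor how lack of response applies to BSC, so the net direction is open.

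**What to change.** 1. **EFS start.** Define EFS from the date of randomization in all arms of both parts. For a BSC patient who enters Part I, this is the second randomization for the Part I analysis. Cost: wording, and drug-arm EFS lengthens by the days from randomization to first dose.
2. **Calendar schedule.** State the blood count and the transfusion and growth-factor record every 4 weeks (+/- 7 days) for all four Part II arms. Cost: a monthly count and transfusion query in BSC.
3. **Sensitivity analysis.** Without requiring extra BSC marrows, analyze Part II EFS leaving out progression first detected only by a scheduled marrow or cytogenetic test, and report such progression separately. State how patients are followed after it. Cost: recording how each progression was first detected, and one further analysis. It shows the effect on the final comparison but does not correct allocations already made.
4. **Re-entry.** State that BSC patients entering Part I complete the existing Section VI baseline at the second randomization. Cost: wording if that is already intended; otherwise the baseline tests, including a marrow if none falls in the window, for about 30 patients.

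In the same edit, state whether and how lack of response counts as an event on BSC. Without that, the direction of any remaining bias cannot be judged.
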